The *primary objective* of our study is to determine the effectiveness of serial infusions of intravenous (IV) ketamine in adults *with treatment resistant depression (TRD) - diagnosed with either Major Depressive Disorder or Bipolar Disorder* - at a slower infusion time than reported in previous studies. We expect that this approach alongside with the presence of a psychiatrist with Advanced Cardiac Life Support (ACLS) training will eliminate the need for continuing anesthetic monitoring during infusion, thus leading to a more cost-effective intervention. As part of this objective, we plan to recruit 30 individuals with Treatment Resistant Depression and conduct an open label, naturalistic study using slow infusions of ketamine over a time period of 40 minutes. **The duration of this study will be 12 weeks and will include twice weekly infusions over a period of 4 weeks and weekly infusions for the following 4 weeks of the study treatment period (8 weeks). There will also be a 4 week observational period post- treatment.**

Our *hypotheses* are that patients suffering from TRD receiving weekly slow IV infusions of ketamine (0.5 mg/kg) over 40 minutes will:

1. Report similar efficacy and better tolerability than those reported with conventional schemes of 3 infusions per week over a 12 day period.
2. Report less psychiatric side effects measured by changes in test scores on the Montgomery-Åsberg Depression Rating Scale (MADRS), Quick Inventory of Depressive Symptomatology (QIDS) and Young Mania Rating Scale (YMRS) compared to those previously reported with conventional schemes of serial ketamine infusions.
3. Report an almost immediate effect based on the PANSS and Q-LES-Q scales which will be administered after the 40 min infusion period.
4. Report less suicidal ideation measured by changes in scores on the Scale for Suicide Ideations (SSI; Beck et al., 1979), and the Suicide Status Form (SSF; Conrad et al., 2009) scores compared to that previously reported with conventional schemes of serial ketamine infusions.
5. Report a better global outcome of treatment measured by a decrease in scores on in the Clinical Global Impression Scale (CGI; Guy, 1976) score compared to that previously reported with conventional schemes of serial ketamine infusions.
6. Experience less hemodynamic changes in blood pressure and heart rate compared to than those previously reported with conventional schemes of serial ketamine infusions.

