7. Experience no cognitive impairment on the Brief Assessment of Cognition in Affective Disorders (BAC-A) following ketamine infusions. To our knowledge this hypothesis has not been previously assessed after an 8-week serial ketamine infusion treatment period.

Clinical relevance

Treatment Resistant Depression (TRD) is a major public health problem that constitutes a great burden for patients and mental health providers because of its prevalence, impact on people's quality of life and overall cost to the society (Nemeroff et al., 2007). Given the dearth of the research in the field of Ketamine treatment, more naturalistic follow-up studies focusing on ketamine's innovative antidepressant properties are warranted. Further, the findings of this study will provide health professionals with additional knowledge on the antidepressant properties of repeated ketamine IV infusions in both resistant Major Depressive Disorder (MDD) and Bipolar Disorder (BD). The current study will also help characterize responders from non- responders to ketamine, and will enable the assessment of the response and remission rates following ketamine intervention.

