The BAC-A is based on the Brief Assessment of Cognition in Schizophrenia (BAC-S). The BAC-S has been validated both linguistically and psychometrically in a number of psychiatric populations, including patients with schizophrenia and BD (Cuesta et al., 2011; Hill et al., 2013; Kuswanto, Sum, & Sim, 2013; Salgado et al., 2007; Segarra et al., 2011). It has been shown to be as valid and sensitive as a traditional neuropsychological assessment and takes approximately 35 minutes to administer (Keefe et al., 2004; Velligan et al., 2004). Six of the 8 subtests of the BAC-A match those found in the BAC-S. These tests are the Token Motor Task, Symbol Coding, List Learning, Digit Sequencing Task, Category Instances (Animals) and

Controlled Oral Word Association Test (F and S-words), Tower of London (Keefe et al., 2004). In addition to these 6 subtests the BAC-A comprises the Emotion Inhibition Test (a modified version of the Emotional Stroop task (LaMonica, Keefe, Harvey, Gold, & Goldberg, 2010; Williams, Mathews, & MacLeod, 1996)) and the affective auditory verbal learning test (Affective interference test). The latter task is similar to the Affective Auditory Verbal Learning Test (AAVLT) (Snyder & Harrison, 1997). Assessments will be conducted prior to the treatment period, 4, and 8 weeks into the treatment. To avoid potential learning bias we will use parallel versions of the word lists for the Emotion Inhibition Test, Tower of London, and the Verbal Memory Tests to assess cognitive changes over the course of the ketamine treatment.

Study design

We will follow an AB design and clinical/cognitive assessments will be taken at baseline, week 4, week 8, and week 12. Given the preliminary nature of this treatment study this open label trial aims to generate an effect size for a subsequent RCT and/or future grant application. No *a priori* estimates of the power/effect size were therefore calculated.

Timeline	After Each Infusion	Baseline	Week 4	Week 8	Weekly Follow-up Phone Calls	Week 12
SCID-I		X				
Clinical scales (MADRS, CGI, YMRS)		X	X	X	X	X
PANAS, Q-LES-Q, self-report	X					
BAC-A		X	X	X		X
Blood tests/Sample		X	X	X		X
Urine drug test	X	X				

Study sample

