Normality assumptions for continuous variables will be examined. Where appropriate, outliers will be winsorised and log, square root or reciprocal transformations applied to achieve normality if appropriate. If normality cannot not been achieved, either untransformed or dichotomized scores were used. Baseline characteristics will be compared between responders and non-responders with the Mann-Whitney U test for continuous variables and the chi-square test for categorical variables. Changes between two time-points for continuous variables were tested with paired t tests, and associations between continuous variables will be quantified with the Spearman correlation coefficient. Random effects models will be performed to quantify changes in clinical score and its component items over time and to compare temporal differences between eventual responders and non-responders. Splines will be used to determine differences in the pattern of response over time among all patients and to identify the time at which there was no additional improvement in depressive symptoms. Additionally, the relationship between response status between baseline and end of study calculating sensitivity, specificity, and positive and negative predictive values will be reported. Time to relapse for patients who met response criteria at end point will be estimated with the Kaplan-Meier method. Analyses will be performed with IBM SPSS Statistics (version 19; SPSS, Chicago, Illinois) and SAS (version 9.2; SAS, Cary, North Carolina).

Study timetable

Activities	Months											
	1	2	3	4	5	6	7	8	9	10	11	12
Obtain IRB approval at UTHealth and HCPC		x	x									
Set up the Ketamine Ambulatory Clinic at HCPC			x	x								
Start recruiting patients and collecting data					x	x	x	x				
Analyses of initial dataset								x	x	x		
Submit a poster to International meeting with final results									x	x	x	
Submit result to high-impact peer-reviewed journals											x	x

Importance of the knowledge to be gained

Our findings will enhance our understanding of the safety, tolerability and efficacy of ketamine infusion in adults with TRD. Further it will help us understand the feasibility of this treatment in a psychiatric setting. The findings of the present study will also constitute an important foundation for future grant proposals investigating the efficacy of this intervention as a measure of suicide prevention.

*Women and Minority Inclusion in Clinical Research**Inclusion of Women*

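### Hypothesis 7 predicts no cognitive impairment, but the only listed method that covers BAC-A change is a paired t test with no margin, and its non-significance cannot show absence of decline

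*Combined protocol and SAP*

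**What the plan says.** The last of the seven hypotheses is that patients will "Experience no cognitive impairment on the Brief Assessment of Cognition in Affective Disorders (BAC-A) following ketamine infusions". The protocol adds: "To our knowledge this hypothesis has not been previously assessed after an 8-week serial ketamine infusion treatment period". It does not say what size of decline counts as impairment, on which BAC-A score, or at which visit.

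The Data analysis section does not mention the BAC-A or cognition. Its general rule is: "Changes between two time-points for continuous variables were tested with paired t tests". It also says: "Random effects models will be performed to quantify changes in clinical score and its component items over time". Those models are named for clinical scores, the splines are named for depressive symptoms, and neither carries a margin.

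Under Study design: "We will follow an AB design and clinical/cognitive assessments will be taken at baseline, week 4, week 8, and week 12". There is one arm ("we plan to recruit 30 individuals with Treatment Resistant Depression"), and no a priori "estimates of the power/effect size were therefore calculated".

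Under Cognitive assessment, the protocol acts against learning bias: "we will use parallel versions of the word lists for the Emotion Inhibition Test, Tower of London, and the Verbal Memory Tests". No parallel version is mentioned for the Token Motor Task, Symbol Coding, Digit Sequencing or the fluency tasks.

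Under Non responders, patients without a 30% fall in MADRS by the 4th treatment leave the study.

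**The concern.** A paired t test takes no change as its null hypothesis. It can reject that null but cannot establish it. With nothing else listed for the BAC-A, the only test outcome compatible with hypothesis 7 is a failure to find a significant decline. That outcome becomes more likely as fewer patients are analysed, so a weaker study looks more supportive.

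Two features of the design add to this. Patients can sit the battery up to four times, and without a control group any practice gain cannot be separated from a drug effect. In addition, two infusions a week put the 4th treatment at about week 2. Non-responders therefore leave before the week 4 BAC-A, and the plan describes no cognitive assessment at removal. The number analysed will fall below 30 if anyone is removed, and those who stay are selected for improved mood. The background section itself says that cognitive gains in a cited ketamine study may have reflected reduced depressive severity.

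At stake is a statement about cognitive safety over an 8-week course, a question that the protocol presents as new.

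**Working it through.** The plan has no power, alpha or precision figure for the BAC-A, so there is none to reproduce. The calculations below are illustrations.

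**Inputs.** From the documents: 30 patients, one arm, paired t test, BAC-A at baseline and weeks 4, 8 and 12, removal of non-responders by the 4th treatment. Assumed: two-sided 5%; true declines d in units of the SD of the change score; 30, 20, 18 or 15 patients analysed, because no removal rate is given.

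**1. Chance that a true decline is not significant.** With n pairs, t follows a noncentral t distribution with n − 1 degrees of freedom and noncentrality −d√n. The chance of no significant decline is 1 − P(t < −t(0.975, n−1)). For d = 0.4 and n = 30, the noncentrality is −0.4 × √30 = −2.19, the critical value is 2.045, and the chance is 0.437.

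**2. Precision.** The 95% half-width in SD of change is t(0.975, n−1)/√n. For n = 30 this is 2.045/5.477 = 0.37.

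| n analysed | d = 0.2 | d = 0.3 | d = 0.4 | d = 0.5 | 95% half-width (SD) |
|---|---|---|---|---|---|
| 30 | 0.816 | 0.645 | 0.437 | 0.246 | 0.37 |
| 20 | 0.867 | 0.754 | 0.603 | 0.436 | 0.47 |
| 15 | 0.892 | 0.810 | 0.697 | 0.562 | 0.55 |

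The last column also shows that an observed mean decline of just under 0.37 SD with 30 patients, or just under 0.47 SD with 20, would be non-significant.

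**3. Practice gain.** The protocol counts 8 subtests. If its Verbal Memory Tests are List Learning and the affective verbal learning test, parallel versions are named for 4 (with Emotion Inhibition and Tower of London) and not for the other 4. The documents give no size for practice gain. Suppose that it is 0, 0.1 or 0.2 SD against a true 0.4 SD decline. The net decline is then 0.4, 0.3 or 0.2 SD. From the n = 30 row, the chance of no significant decline is 0.437, 0.645 or 0.816.

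**4. What a confidence-bound rule would deliver.** Success means that the lower bound lies above minus the margin m. With no true change, the chance of success is P(T > t(1−α, n−1)), where T is noncentral t with noncentrality m√n.

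| Margin | One-sided level | n = 30 | n = 18 |
|---|---|---|---|
| 0.5 SD of change | 5% | 85% | 65% |
| 0.5 SD of change | 2.5% | 75% | 52% |
| 0.5 baseline SD, correlation 0.3 | 5% | 73% | 53% |
| 0.5 baseline SD, correlation 0.8 | 5% | 99% | 94% |

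The unit matters. With equal variances and test-retest correlation r, the SD of change is the baseline SD × √(2(1 − r)). A margin of 0.5 baseline SD is therefore 0.5/√1.4 = 0.42 SD of change at r = 0.3, 0.5/√1 = 0.50 at r = 0.5 and 0.5/√0.4 = 0.79 at r = 0.8. The two units agree only at r = 0.5.

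**The case against.** The strongest reply is that this is a pilot. The protocol calls the study preliminary, says that it aims to generate an effect size, makes MADRS remission the primary outcome, and calculates no power. A reader might infer that the plan will treat a non-significant t test as proof of cognitive safety. The documents do not support that: no decision rule is written for hypothesis 7, and the remark on novelty says only that the question had not been assessed before. The supportable statement is that non-significance could be read as support. A paired analysis can also be reported as a mean change with an interval, which would suit the stated aim.

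It is equally tempting to say that practice effects are ignored, or that they will cancel a decline. Neither follows. Learning bias is addressed for part of the battery, and the absence of parallel versions elsewhere is inferred from silence. No practice effect is quantified, so the most that can be said is that it could mask a decline.

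The random effects models might be thought to fill the gap. They are named for clinical scores, and extending them to the BAC-A would still leave no margin.

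The size of the problem also rests on assumed inputs throughout. What stands after all this is that hypothesis 7 is a stated prediction of absence, that impairment is undefined, and that the one applicable method cannot support the prediction. The pilot label is an argument for estimation, not for a significance test.

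**Conclusion.** The point holds in this limited form. As written, hypothesis 7 has no criterion by which it could be supported, and failure to reject equality in at most 30 uncontrolled patients must not serve as one. In the illustrations, a decline of 0.4 SD of change would go undetected in 44% to 70% of trials for 30 down to 15 patients analysed, and the interval would reach 0.37 to 0.55 SD on either side of the estimate. These figures depend on two-sided 5%, the assumed decline and the assumed numbers analysed. The direction of the problem does not depend on them. The documents do not show that the investigators intend to claim proof of safety, or how large practice gain would be. The change should be made, because it is cheap and decides what may be said about cognition.

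**What to change.** In the Data analysis section, name one BAC-A summary score and week 8 as its time point. Report the mean change from baseline with its confidence interval and the number analysed. Then choose one of two routes:

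- **Margin.** State in advance one justified margin, in a single unit (baseline SD or SD of change), applied to that same score, together with the confidence level. Claim no impairment only if the bound excludes the margin, and otherwise report the result as inconclusive.
- **Estimation only.** Label hypothesis 7 as estimation and draw no conclusion of absence.

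On either route, state that a non-significant paired t test will not be read as absence of impairment. Report subtests without parallel versions separately, with a caution about practice gain. A margin does not remove that gain, and parallel versions do not remove familiarity with the task.

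Reconcile the visit lists at the same time: the Cognitive assessment text gives pre-treatment, week 4 and week 8, while the Study design sentence and the timeline add week 12.

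The cost is a few lines of text and no new data. The downside is that the margin route may end inconclusive, with the chances of success shown in the second table above.

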2.0 Research Strategy

A. Significance

Background and Rationale

Major psychiatric disorders such as major depressive disorder (MDD) and bipolar disorder (BD) are among the most disabling mental illnesses worldwide with a global social cost of \$66.5 million and 16.8 million disability-adjusted life years (DALYs) respectively (Collins et al. 2011). MDD is a chronic and disabling mental illness (Kessler et al., 2005a, 2005b; Murray et al., 2012), associated with increased mortality and shortened lifespan (De Hert., et al. 2011; Ferrari et al., 2013; Whiteford et al., 2013). Likewise, BD is one of the most severe and lethal psychiatric disorders (Nock et al., 2009; Nordentoft et al., 2011). The lifetime prevalence of BD is approximately 4% in the United States (Merikangas et al., 2007) with depressive symptoms dominating the longitudinal course of the illness (Calabrese et al., 2008; Judd et al., 2002, 2003).

A growing body of evidence has revealed that most patients with MDD who receive evidence-based treatments do not achieve sustained remission with first-line antidepressants (McIntyre et al., 2014). Treatment resistant depression (TRD) is generally defined as a reduced clinical response to adequate doses and duration of antidepressants (Dodd et al., 2005; Fava, 2003; Hauptman et al., 2008; Rush et al., 2003). Similarly, treatment resistance in bipolar depression refers to the lack of response to adequate trials of monotherapy with lithium or lamotrigine or the combinations of these two mood stabilizers with anticonvulsants or antipsychotics (Lipsman et al., 2010) and non-remission despite receiving three adequate trials of first line medications with mood stabilizing properties (Malhi et al., 2012).

In spite of the advances in the treatment of depression (which includes new-generation antidepressants and multimodal treatment strategies (combining mood stabilizers, atypical antipsychotics, hormone supplementation, and psychosocial interventions), treatment resistant depression remains a significant problem in the clinical management of MDD and BD (Gaynes et al., 2009; Nelson et al., 2009; Spielmans et al., 2013; Warden et al., 2007; Zarate et al., 2013b, Prudic et al., 2013, Rabheru et al., 2012). Furthermore, the time lag in onset of therapeutic effect limits treatment response and adherence in bipolar depression (Calabrese et

al., 2006; Thase et al., 2006; Weisler et al., 2008). The additive effects of all these factors increase the overall risk for comorbidity and suicidality (Jick et al., 2004; Machado-Vieira et al., 2008).

The antidepressant properties of ketamine, an anesthetic agent with N-methyl-D-aspartic acid receptor (NMDAR) antagonist properties has been demonstrated in MDD, bipolar depression, and TRD (Abdallah et al. 2012; Diazgranados et al. 2010a; Kranaster et al. 2011; Kudoh et al. 2002; Murrough et al. 2013a,b; Okamoto et al. 2010; Zarate et al. 2012). Further, a recently published meta-analysis has confirmed the efficacy of intravenously administered ketamine in depressive disorders independently from the severity, refractoriness or specificity of the depressive disorder (Fond et al., 2014). However, there is some reluctance to use ketamine in the clinical practice due to the potential concerns of misuse (Morgan and Curran 2011) dosage, side effects, duration of efficacy, and impact on suicidal ideations.

The results of the largest study conducted thus far on the antidepressant effects of repeated ketamine infusions included twenty-four subjects with TRD who underwent a washout of antidepressant medication followed by a series of up to six intravenous (IV) infusions of ketamine (0.5 mg/kg) over 40 minutes administered open-label three times weekly over a 12- day period (Murrough et al., 2013b). The TRD patients meeting response criteria were monitored for depressive relapse for up to 83 days from the last infusion. The antidepressant effect of ketamine was evident very early in the course of treatment. Moreover, ketamine exerted a broad-spectrum effect on individual symptoms of depression, and rapid response to the first infusion was highly predictive of a sustained response to subsequent infusions (Murrough et al., 2013b). Although preliminary, ketamine's large and sustained effect size regarding its antidepressant properties seems to be carried over repetitive IV infusions. In particular, suicidal ideation (SI) rapidly decreases even among non-responders to repetitive ketamine IV infusions. Therefore, ketamine is suggested to exert a unique anti-SI effect even in the absence of a full antidepressant response (Murrough et al., 2013b). This finding is consistent with previous reports highlighting the potential anti-SI effects of single dose infusion of IV ketamine in depressed populations (Diaz-Granados et al., 2010b; Larkin and Beautrais, et al 2011; Price et al., 2009).

Recently, researchers at the Mayo Clinic have performed serial ketamine infusion but at a lower infusion rate (Rasmussen et al., 2013). Ten depressed patients were treated with twice weekly

infusions of ketamine 0.3 mg/kg administered over 100 min until either remission was achieved or four infusions were given. Patients were naturalistically followed weekly for four weeks after completion of the infusions and psychiatric side effects were assessed with the Young Mania Rating Scale (YMRS; Young et al., 1978) and the Brief Psychiatric Rating Scale (BPRS; Overall and Gorman, 1988) respectively. While a 50% remission rate was documented without any significant increase on BPRS or YMRS measures, only two patients maintained remission at the 4-week follow up session. Nonetheless, it seems that ketamine infusions at a lower rate than previously reported might produce similar efficacy, excellent tolerability, and thus may be more available for routine clinical care.

Ketamine infusions do not appear to have negative neurocognitive sequels. In a recent study, 15 patients with TRD underwent six IV infusions of 0.5 mg/Kg ketamine over 40 min, (three times a week during a 12-day period) followed by a 4-wk observational period. Following the last ketamine infusion the authors observed an improvement in visual memory and working memory. These cognitive changes may have been due to the decrease in the severity of the depressive symptoms (Shiroma et al. 2014). Along the same line, Murrough et al. (2015) found no change in cognitive functioning 7 days post-ketamine treatment in individuals with treatment-resistant depression.

To the best of our knowledge, the only published study exploring the tolerability, safety, and efficacy of repeated-dose open-label IV ketamine (six infusions over 12 days) focused on 10 medication-free symptomatic patients with TRD who had previously shown a meaningful antidepressant response to a single ketamine dose (Aan het Rot, et al., 2010). Patients received a 40-min IV infusion of ketamine (0.5 mg/kg) in an inpatient setting with continuous vital-sign monitoring and repeated recording of adverse events such as psychotomimetic effects. In the event that patients showed a 50% reduction in MADRS scores on day 2, they received five additional infusions on an outpatient basis on days 3, 5, 8, 10, and 12. Follow-up visits were conducted twice weekly for 4 weeks or until relapse. Ketamine elicited minimal transient positive psychotic or dissociative symptoms. Side effects during and after each ketamine infusion although common were reportedly mild. The response criterion was met by nine patients after the first infusion as well as after the sixth infusion of ketamine. MADRS scores after the sixth ketamine infusion were reduced by 85%, and an 89% relapse rate was reported between weeks 3 and 4 after finishing repeated IV ketamine infusion.

To summarize, these findings confirm the feasibility of low concentration and slower infusion rate of repeated-dose IV ketamine infusions for the acute treatment of TRD in the clinical practice (Aan het Rot, et al., 2010; Murrough et al., 2013b; Rasmussen et al., 2013).

Thus, in the current study we want to naturalistically explore the antidepressant effects of serial slow IV infusions (40 minutes) of ketamine at a dose of 0.5 mg/kg, over a treatment period of 8 weeks in an academic psychiatric hospital. This is a minimal sedation treatment. This dosage is the highest used so far in the literature and was selected because of its reported benefits in a psychiatric population. The dosage will be calculated using the patient's weight in kilograms. For dosing purposes, 0.5-0.9 round up to the next dose and from .01-0.49, we will round down to the lower dose. The primary outcome measure of this study will be *remission* estimated based on the severity of depressive scores (MADRS). After the 8 weeks of treatment, there will be a four week observational period. During the observational period, participants will receive treatment as usual and will be contacted over the phone for follow-up questions regarding their overall health status, mood and clinical state using MADRS, YMRS and CGI. They will also complete a neurocognitive task at the end of the 4 week observational period.

B. Innovation

The approach taken in the current study is novel for two reasons: 1) we are testing a novel dosage and time of infusion for the administration of slow infusion, repeated IV ketamine targeting TRD; 2) this is the first naturalistic study of repeated ketamine IV infusion for MDD and BD in a psychiatric setting. Furthermore, this will constitute the largest study conducted to date testing the antidepressant effects of repeated ketamine infusions in a combined population of MDD and BD patients with TRD.

C. Approach

The current project will exploit the feasibility of recruitment associated with ongoing studies at the University of Texas, Center of Excellence on Mood Disorder, Department of Psychiatry and Behavioral Science in Houston aimed at identifying the neural correlates of BD. The clinical sample will include individuals from various ethnic/racial backgrounds, reflecting the local community in the greater Houston area. We will use slow infusions of ketamine over a time

period of 40 minutes. **We will conduct an open label, naturalistic study focusing on the antidepressant effects of ketamine twice a week for the first 4 weeks and then weekly injections up to week 8 in an academic psychiatric hospital (UTHealth Harris County Psychiatric Center - HCPC).** Thirty patients with clinically documented TRD will be screened for diagnosis with the depression and bipolar disorder subset of the Structured Clinical Interview for DSM-IV (SCID) (First et al., 1996) at baseline to establish the presence of a major depressive episode.

The administration of ketamine and urine tests will be carried out at the UTHealth Harris County Psychiatric Center (HCPC) in Houston, Texas. Routine blood tests and clinical/cognitive assessment will be done at the UTHealth Harris County Psychiatric Center (HCPC). Study drug will be provided in identical syringes, containing clear solutions including 1 mL of ketamine, e.g. 100 mg/mL with 9 mL of normal saline. A syringe will be used to provide IV applications of solution (). An ACLS psychiatrist will monitor the patient at HCPC. The administration of ketamine will be initiated by the anesthesiologist. The anesthesiologist will be present during the ketamine administration (40 minutes) and post-procedure (until patient is awake and anesthesiologist deems patient is clinically stable. The infusions will be conducted in our hospital during the mornings in a room set specially for this study. During the infusion, patients will be asked constantly about -how they feel and will receive constant attendance from a psychiatric nurse and the attending ACLS- trained psychiatrist. ECG and pulse oximetry monitoring will be maintained throughout the infusions to check for hemodynamic changes.

After completion of each 40 minute infusion, patients will rest for 2 hours under observation of the clinical nurse before being discharged to a responsible adult who will accompany the patient home. Based on Zarate et al.'s (2012)'s protocol infusions will be administered twice a week, every 3 days for the first 4 weeks of the treatment period.

Routine blood tests will be performed in fasted state before the first ketamine infusion, prior to infusions at week 4 and at week 8. These tests aim to test the participants' overall health state. Blood samples will also be used for genetic testing and to measure levels of inflammatory markers. Samples will be stored at [REDACTED]. As stated in the consent form, participants will not receive any medical results or genetic counseling by providing a sample. All participants will undergo urine drug tests before each ketamine infusion.

Clinical questionnaires (e.g. MADRS) will be administered at baseline, at weeks 4, 8, and Week 12. The PANSS and Q-LES-Q scale will be administered after each ketamine infusion is completed. During the course of infusions, patients will receive treatment-as-usual from their primary psychiatrists as would be the case in a traditional therapeutic setting. There will be no changes in medication regimen throughout the 8 week treatment period as well as the 4 week observational follow-up period. Participants will be provided with a contact card directing them to the nearest ER/physician in case of emergency. Participants will be contacted weekly during the 4 week observational period to review the patient's health status and administer clinical scales. Upon conclusion of the intervention patients will be offered the opportunity to come back for maintenance sessions. The frequency of these sessions will depend on the patient's wishes and the physician's clinical judgment. The maximum session frequency will be once every month for a maximum of 12 months.

Assessment

The protocol consists of two components: clinical and cognitive assessments.

Clinical assessment

This evaluation will obtain family history and demographic data. Copies of any recent medical evaluations (past medical history, physical exam, etc.) will be requested from treating clinicians and health care providers. We will perform a urine drug screening (UDS) to rule out recent undisclosed use illicit substances. Demographic information is obtained through a standardized form and covers: age, race, gender, education (information both on siblings and their parents), religion, and socioeconomic status. Participants will fill out mood questionnaires rating the severity of the clinical symptoms.

-MINI Interview: This is the standard psychiatric research evaluation for ascertainment of psychiatric diagnosis in the context of research studies (Sheeha et al., 2016)). It is a comprehensive structured interview for determining axis I diagnosis according to the DSM-V.

-Clinical Global Impression Scale (CGI): This is a clinical instrument to assess global changes in patients' status in clinical studies. We will use the CGI-BD, for use with BD patients (Guy et al., 1976).

-Montgomery-Åsberg Depression Rating Scale (MADRS): this scale rates depressive symptoms, and its psychometric properties are well-established (Montgomery et al. 1979).

-Young Mania Rating Scale (YMRS): This is a well-established clinical severity rating scale for manic symptoms that has adequate inter-rater reliability and internal consistency (Young et al., 1978).

- Quality of Life Enjoyment and Satisfaction Questionnaire (Q-LES-Q): this scale is patient-reported and measures the degree of enjoyment and satisfaction experienced by subjects in various areas of daily functioning (Endicott et al., 1993).

-

- The Positive and Negative Syndrome Scale (PANSS) includes 30- items and was conceived as an operationalized, drug-sensitive instrument that provides balanced representation of positive and negative symptoms. It is composed of four scales measuring positive and negative syndromes, their differential, and general severity of illness. The Positive and Negative Syndrome Scale (PANSS) for Schizophrenia. Kay, Stanley R.; Fiszbein, Abraham; Opfer, Lewis
A. Schizophrenia Bulletin, Vol 13(2), 1987, 261-276. This scale will be administered following each ketamine infusion to assess acute changes in mood.

Self-report questionnaires to assess mood and anxiety:

1. Adult (Brief Dissociative Experiences Scale [DES-B]—Modified): Frequency: After every injection, to monitor the dissociative side effects, Scale features: simple, easy to use, new DSM-5 self-rated scale
2. Severity Measure for Generalized Anxiety Disorder—Adult : Every 4 weeks, to measure the severity of anxiety. Scale features: simple, easy to use, new DSM-5 self-rated scale
3. Snaith–Hamilton Pleasure Scale: every 4 weeks, to measure the level of anhedonia, Scale features: easy to use, used before in ketamine studies, self-rated scale

Cognitive assessment

The BAC-A is based on the Brief Assessment of Cognition in Schizophrenia (BAC-S). The BAC-S has been validated both linguistically and psychometrically in a number of psychiatric populations, including patients with schizophrenia and BD (Cuesta et al., 2011; Hill et al., 2013; Kuswanto, Sum, & Sim, 2013; Salgado et al., 2007; Segarra et al., 2011). It has been shown to be as valid and sensitive as a traditional neuropsychological assessment and takes approximately 35 minutes to administer (Keefe et al., 2004; Velligan et al., 2004). Six of the 8 subtests of the BAC-A match those found in the BAC-S. These tests are the Token Motor Task, Symbol Coding, List Learning, Digit Sequencing Task, Category Instances (Animals) and

Controlled Oral Word Association Test (F and S-words), Tower of London (Keefe et al., 2004). In addition to these 6 subtests the BAC-A comprises the Emotion Inhibition Test (a modified version of the Emotional Stroop task (LaMonica, Keefe, Harvey, Gold, & Goldberg, 2010; Williams, Mathews, & MacLeod, 1996)) and the affective auditory verbal learning test (Affective interference test). The latter task is similar to the Affective Auditory Verbal Learning Test (AAVLT) (Snyder & Harrison, 1997). Assessments will be conducted prior to the treatment period, 4, and 8 weeks into the treatment. To avoid potential learning bias we will use parallel versions of the word lists for the Emotion Inhibition Test, Tower of London, and the Verbal Memory Tests to assess cognitive changes over the course of the ketamine treatment.

Study design

We will follow an AB design and clinical/cognitive assessments will be taken at baseline, week 4, week 8, and week 12. Given the preliminary nature of this treatment study this open label trial aims to generate an effect size for a subsequent RCT and/or future grant application. No *a priori* estimates of the power/effect size were therefore calculated.

Timeline	After Each Infusion	Baseline	Week 4	Week 8	Weekly Follow-up Phone Calls	Week 12
SCID-I		X				
Clinical scales (MADRS, CGI, YMRS)		X	X	X	X	X
PANAS, Q-LES-Q, self-report	X					
BAC-A		X	X	X		X
Blood tests/Sample		X	X	X		X
Urine drug test	X	X				

Study sample

We will recruit adult patients aged 18-65 years with MDD or BD, with documented TRD (according to DSM-IV TR), and who have failed (defined as patient does not reach remission within the 8 week trial of an antidepressant or combination at a therapeutic dose) of at least two trials of first line evidence-based treatments and/or ECT.

Exclusion criteria

- 1) Being younger than 18 of age or older than 65.
- 2) Diagnosed with intellectual disability, e.g. mental retardation (MR), neurodegenerative diseases, e.g. early-onset neurocognitive disturbances such as frontotemporal dementia (FTD) or behavioral disorders, e.g. adult onset Attention Deficit Hyperactivity Disorder (ADHD).
- 3) Diagnosed with BD-NOS or rapid cycling BD
- 4) Diagnosed with personality disorders (PD).
- 5) Previously or currently diagnosed with psychosis (schizoaffective disorder - SAD) or schizophrenia - SCZ).
- 6) Current major medical problems that affect brain anatomy, neurochemistry, or function, e.g., obstructive sleep apnea requiring Continuous Positive Airway Pressure (CPAP), liver insufficiency, kidney insufficiency, cardiovascular problems, systemic infections, cancer, auto-immune diseases, and any brain disorder (seizure disorder, stroke, dementia, degenerative neurologic diseases); history of any brain diseases, including seizures, stroke, meningitis, encephalitis, dementia, degenerative brain diseases, and head injury with loss of consciousness for any period of time.
- 7) Diagnosed specifically with a cardiovascular disorders such as Arrhythmias, Chronic Heart Failure, Myocardial Infarction (MI) or suffering from Chronic Obstructive Pulmonary Disease (COPD) or asthma. Suffering from uncontrolled hypertension or diastolic BP over 100. Cardiac clearance prior to enrolling in the study/medical records from physician will be required *per patient's PCP*. (Diastolic BP must be less than 100 Systolic BP less than 165 and greater than 85 Heart rate less than 100.)
- 8) Patients with thyroid condition and are not currently euthyroid or on stable treatment regimen.
- 9)
- 10) Patients with increased risk of laryngospasm, active upper respiratory infections, respiratory depression, increased intracranial pressure, hyperthyroidism, or porphyria.

- 11) Current substance abuse or dependence. Only patients who achieved stable, full remission for at least 6 months will be included.
